The analyses will initially focus on the study completers to compare telehealth PC with in-person PC in patients who completed the protocol as intended without imposing assumptions about missing data. We will also use the intention-to-treat (ITT) principle with all randomized subjects, conducting sensitivity analyses to explore how various assumptions about missing data and differences between completers and non-completers affect the estimated outcomes. If data appear to be missing at random, we will employ multiple imputation methods. However, if we find that participants do not complete the study because of disease worsening, suggesting that data are not missing at random, we will employ terminal decline joint modeling approach, under the direction of the study statistician. The advantage of the terminal decline approach is that it models the trend in participant-reported outcomes backward from the time of the patient's death rather than prospectively from the time of enrollment. Thus, this approach controls for the known relationship between patient and caregiver QOL deterioration as the patient's death approaches. Notably, the terminal decline approach also accounts for missing outcome data. It utilizes a mixed-effects model for the longitudinal outcomes to provide valid and efficient estimates for missing outcome data. We will analyze the terminal decline and survival distributions with semiparametric models applied to both groups. Based on the fitted models, we will compare participant-reported outcomes at specified times before death (one, three, and six months prior to the patient's death). All models will adjust for baseline criterion scores, and any potential imbalances between the two groups. The terminal decline joint modeling approach has been utilized in multiple prior PC studies given its ability to account for deterioration in outcomes closer to death.⁵⁹

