Sample size calculations were performed to demonstrate equivalence with a margin of ±4 points on the FACT-L at week 24, assuming a standard deviation of 17.5 points and a between-group difference of 0 points. 469 patients per group would achieve 95% power at a 5% significance level using two one-sided, equal-variance t-tests. To account for an anticipated 33% missing data proportion at week 24 due to loss-to-follow-up, withdrawal, or death, enrollment of 625 per group (1250 total) was planned.

9. General Statistical Considerations

Statistical Software

All statistical analyses will be performed using SAS (SAS Institute Inc., NC, USA) and R (R Foundation for Statistical Computing, Vienna, Austria).

Analysis Population

The primary analyses will be conducted according to the intention-to-treat principle. All randomized patients will be included and analyzed in the group to which they were initially randomized, regardless of intervention adherence. To address intervention contamination introduced during the COVID-19 pandemic, sensitivity analyses will be conducted to ensure the validity of the study findings. These sensitivity analyses may include per-protocol analysis, contamination adjusted intention-to-treat analysis using instrumental variables, and inverse probability weighting analyses to provide robust statistical estimates for the primary and secondary outcomes in this trial.

Patient Disposition

The flow of patients through the study will be demonstrated using a flow diagram, consistent with the Consolidated Standards of Reporting Trials (CONSORT) statement. This diagram will display number of patients assessed for eligibility, the number of patients who enrolled and randomized in the study and the number of patients who were excluded or otherwise not enrolled. For enrolled patients, the study group allocation will be displayed, along with the number of patients who complete follow-up assessments at each time point. The number of patients in each group who were lost to follow-up or otherwise excluded from analysis will be displayed.

Baseline Characteristics

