Baseline characteristics including demographic information, smoking status, cancer type, comorbidities, and baseline PROs score will be summarized by intervention group using descriptive statistics and visual displays. Descriptive statistics for continuous variables will include the number of subjects, mean, standard deviation, median, first and third quartiles, and minimum and maximum values for the observed value. Frequencies and percentages will be calculated for categorical variables.

Adjustment of the Intervention Effect

The primary analyses for all outcomes will be unadjusted except when adjustment for baseline outcome values is pre-specified. For the primary outcome, a sensitivity analysis will evaluate the impact of adjustment for study site, the randomization stratification variable (n=20 sites). Adjustment for study site via a main effect or random effect will be considered. Small strata will be combined as needed to ensure numeric stability of model estimates.

For all outcomes, sensitivity analyses will adjust for baseline characteristics that are imbalanced between treatment groups, if needed. Imbalanced characteristics will be identified *a priori* by examining the distributions of baseline characteristics known to be associated with the primary and secondary outcomes by intervention group. Characteristics that are imbalanced to an extent that is considered clinically meaningful will be included as main effects.

Significance Level and Multiplicity Adjustment

Statistical significance testing for equivalence of the primary outcome will use two one-sided tests, each with a type I error rate of 0.05. The Benjamini-Hochberg false discovery rate (FDR) control approach will be used to interpret results of significance tests of secondary outcomes with an FDR of 0.15. Analyses of exploratory outcomes will not be adjusted for multiple comparisons, and presented results will emphasize estimates and confidence intervals.

Scoring of Patient-Reported Outcomes

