Total and subscale scores for patient-reported outcomes will be calculated for each patient/timepoint using published scoring algorithms. When scoring instructions specifically address how missing item responses should be handled in the score calculation, these instructions will be followed. If no specific guidance for handling missing item responses is provided, subscale scores (if applicable) or total scores (for unidimensional scales) will be calculated via single imputation of the mean of observed subscale values if >50% of the subscale items are non-missing. For scales with total scores derived from the sum or average of two or more subscales, the total score will not be calculated unless all subscale scores can be calculated.

Primary analyses of FACT-L scores will utilize the standard published scoring method. Secondary analyses will use an alternative scoring method for surveys that do not meet the above criteria for calculating the total score—i.e., those that have 50% or fewer non-missing responses on one or more subscales. The alternative scoring method allows calculation of the total score if >50% of all items (across all four subscales) are non-missing.

Missing Data

Primary analyses will include available data without imputation of missing data. The characteristics of patients who do versus do not complete the week 24 survey will be compared descriptively. Sensitivity analyses will explore how different assumptions about the missing data mechanisms affect estimated outcomes. These sensitivity analyses may include multiple imputation, terminal decline joint modeling, or partially conditional models, which provide estimates of the mean conditional on being alive and observed at each timepoint.

10. Statistical Analysis

Primary Outcome

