The primary outcome is patient-reported quality of life at week 24, as measured by the FACT-L. The difference in week 24 means between intervention groups will be estimated using a linear regression model with group assignment (telehealth PC vs in-person PC) and baseline FACT-L score as main effects. Using the pre-specified equivalence margin of ±4 points, equivalence of telehealth PC will be established if the 90% confidence interval (CI) for the estimated difference in means is within the equivalence interval (-4, 4). The corresponding p-value for equivalence will be calculated as the larger of the two p-values from two one-sided tests of the estimated difference in means against null values of -4 and 4. Model-based estimates of the mean with 95% CI in each group, the difference in means between groups and its 90% CI, and the p-value will be reported.

To accompany the approach described above, we will also use a linear mixed effects regression model to estimate the difference in week 24 means between intervention groups. This model will

utilize FACT-L scores at baseline, week 12, and week 24, with estimation via maximum likelihood. The model will include fixed effects for group assignment (telehealth PC vs in-person PC), time from baseline (in weeks), and the time-by-group interaction, as well as random intercepts for each patient. A contrast will be used to estimate the difference in means at week 24, and this estimate will be evaluated for equivalence in the same manner described above. This will be reported as a sensitivity analysis for evaluating equivalence for the primary outcome.

Secondary Outcomes

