The proportion of caregiver attendance in PC visits will be compared between groups using a generalized linear mixed effects regression model specified with an identity link function and binomial response probability distribution. The model will include a main effect for group assignment (telehealth vs in-person) and random intercepts for each patient. Superiority of telehealth PC will be established if the nominal p-value for the difference in proportions (against a null value of 0) is significant in favor of telehealth PC after application of the multiplicity adjustment procedure for secondary outcomes. Model-based estimates of the proportion with 95% CI in each group, the difference in proportions between groups and its 95% CI, and the nominal p-value, and the multiplicity-adjusted p-value will be reported.

The difference between groups in the mean patient and caregiver satisfaction with care delivery will be assessed using a linear regression model with a main effect for group assignment (telehealth PC vs in-person PC), separately for patients and caregivers. Superiority of telehealth PC will be established if the nominal p-value for the difference in means (against a null value of 0) is significant in favor of telehealth PC after application of the multiplicity adjustment procedure for secondary outcomes. Model-based estimates of the mean with 95% CI in each group, the difference in means between groups and its 95% CI, and the nominal p-value, and the multiplicity-adjusted p-value will be reported.

Exploratory Outcomes

The rate of change in quality of life from baseline to week 48 (assessed by the FACT-L) will be compared between groups using a linear mixed effects regression model. This model will utilize FACT-L scores at each timepoint, with estimation via maximum likelihood. The model will include fixed effects for group assignment (telehealth vs in-person PC), time from baseline (in weeks), and time-by-group interaction, as well as random intercepts for each patient. Model-based estimates of the slope with 95% CI in each group and the difference in slopes between groups and its 95% CI will be reported.

The following exploratory outcomes will be compared between intervention groups utilizing the same approach:

- Patient coping strategies, as measured by the Brief-COPE Questionnaire
- Caregiver QOL, as assessed by the CARGOQOL
- Caregiver mood, as measured by the HADS
- Patient mood, as measured by the HADS

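### The mixed-model sensitivity analysis of week-24 FACT-L forces a straight-line arm difference, so its week-24 contrast is partly a week-12 result

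*SAP*

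**What the plan says.** SAP Section 10 (Primary Outcome) decides equivalence by a linear regression of week-24 FACT-L on group and baseline score, with the 90% confidence interval read against ±4.

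Beside it stands a linear mixed model, fitted by maximum likelihood to baseline, week 12 and week 24. Its terms are group, "time from baseline (in weeks), and the time-by-group interaction, as well as random intercepts for each patient". The SAP continues: "A contrast will be used to estimate the difference in means at week 24, and this estimate will be evaluated for equivalence". On status: "This will be reported as a sensitivity analysis for evaluating equivalence for the primary outcome".

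No visit category, quadratic or spline term is named. The exploratory week-48 model is worded the same way and reports "Model-based estimates of the slope with 95% CI in each group and the difference in slopes between groups", so time is one linear term.

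Other sensitivity analyses exist. SAP Section 9 has one for adjustment: "For the primary outcome, a sensitivity analysis will evaluate the impact of adjustment for study site". For missing data it says: "These sensitivity analyses may include multiple imputation, terminal decline joint modeling, or partially conditional models".

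**The concern.** The contrast is meant to estimate the week-24 difference. With one slope per arm it estimates the end of a fitted line, which also draws on the week-12 and baseline differences. It hits the week-24 difference only if the arm difference grows in proportion to time, or is zero throughout.

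This matters because of the job the model has. The plan expects 25% (Protocol 7.4) or 33% (SAP Section 8) of week-24 scores to be missing, and the primary analysis uses available data without imputation. In the SAP, this is the only sensitivity analysis for the primary outcome whose method is fixed and which uses scores from patients with no week-24 score. It will be read beside the primary result, against the same margin, as a check on dropout. If the arm difference is not linear in time, a gap between the two analyses can come from the time term instead.

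**Working it through.** Write d0, d12 and d24 for the true arm differences at the three visits.

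**Inputs from the documents.** Margin ±4 and two one-sided 5% tests (SAP Sections 9 and 10); 625 per arm; SD 17.0 (Protocol 7.4) or 17.5 (SAP Section 8); 25% or 33% missing at week 24.

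**Assumed, because the documents give no figure.** Correlations for weeks 0-12, 12-24 and 0-24 of (.65,.65,.5), (.7,.7,.6), (.6,.6,.6) or (.8,.8,.8). Missing at weeks 12/24: 0/0, 15/25% or 18/33%.

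**1. The plan's own figure.** No figure is given for the mixed model. For the primary comparison, power = 2Φ(4/SE − 1.645) − 1 with SE = SD·√(2/469). SD 17.0 gives SE 1.110 and 95.0% (94.9% with the t distribution), which reproduces the stated 95%. SD 17.5 gives 93.6%. Both SDs are carried below.

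**2. Weights, complete data.** A line through three equally spaced visits has its last fitted value at the mean plus half of (last − first):
(d0 + d12 + d24)/3 + (d24 − d0)/2 = −d0/6 + d12/3 + 5·d24/6.
The random intercept does not change this. With d0 = 0 the error is (2·d12 − d24)/6, which is zero only if d12 = d24/2. Maximum likelihood fits to data built with (d12, d24) = (0,4), (2,4) and (4,4) returned 3.33, 4.00 and 4.67. With categorical time all three returned 4.00.

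**3. With dropout.** Under the same completely random pattern in both arms, the error is (1 − w)(2·d12 − d24), where w is the weight on d24. Over the assumed grid w is 0.81-0.83 and the weight on d12 is 0.35-0.38.

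**4. One cell by hand.** Complete data, SD 17, all correlations 0.6. Variance factor: 0.4 × (1 + 4 + 25)/36 + 0.6 = 0.933. SE = 17 × √(2 × 0.933/625) = 0.929. Equivalence needs an estimate below 4 − 1.645 × 0.929 = 2.472.
- (0,4): Φ((2.472 − 3.333)/0.929) = Φ(−0.927) = 17.7%
- (2,4): Φ((2.472 − 4.000)/0.929) = Φ(−1.645) = 5.0%
- (4,4): Φ((2.472 − 4.667)/0.929) = Φ(−2.363) = 0.9%

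**5. Whole grid, true d24 = 4, both SDs, large-sample values.**

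| d12 | expected contrast | declared equivalent |
|---|---|---|
| 0 | 3.23-3.33 | 17-19% |
| 1 | 3.62-3.67 | 10-11% |
| 2 | 4.00 | 5-6% |
| 3 | 4.33-4.38 | 2-3% |
| 4 | 4.67-4.77 | about 1% |

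The primary regression stays at 5% in every row.

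**6. Reverse case, d24 = 0, SD 17.5.** Equivalence is not declared in 1.1-4.5% of trials with d12 = 0, 3.4-9.8% with d12 = 2 and 13-27% with d12 = 4. Cell by cell, the excess over d12 = 0 is 2-5 and 12-22 percentage points. Only that excess comes from the time term. The expected contrasts, 0.7-0.8 and 1.3-1.5, lie well inside ±4.

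**7. Score-dependent dropout** (simulated; depends on the last observed score; SD 17.5).
- Same rule in both arms, d24 = 4: the linear model gives 17-19%, 10-11%, 5-6% and 1% for d12 = 0, 1, 2 and 4. The primary gives 5.0-6.6%, with its estimate moved by at most 0.14. Categorical time with a common baseline gives 5.0%.
- Dropout differing by arm, no true difference: bias is 0.09 to 0.98 for the primary, −0.13 to 0.25 for the linear model and 0.00 to 0.01 for the categorical model.
- Finite-sample check, 2,500 trials, (0,4), 18/33% missing: 18.5% (Monte Carlo SE 0.8 points).

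**8. Actual visit dates.** Dates spread evenly over the ± two-week window (Protocol 5.5.1), complete data: (0,4) gives 3.40 and (4,4) gives 4.60. The error shrinks slightly and remains.

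**The case against.** **The 17-19% is not a trial error rate.** Equivalence rests on the primary regression alone, and a wrong claim backed by both analyses cannot be more frequent than a wrong primary claim. In simulation at (0,4), both passed in 3.5-5.1% of trials. This stands. The percentages describe how often the sensitivity model gives false support or withholds true support.

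**The large effects need strong trajectories.** The SAP plans "assuming a standard deviation of 17.5 points and a between-group difference of 0 points". If there is also no week-12 difference, the time term adds no bias under dropout common to both arms. With 2 points at week 12 the excess failure is 2-5 points. This stands, and no trajectory is documented either way.

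**Where dropout differs by arm, the linear model does better than the primary.** True in the no-difference simulations: at most 0.25 against up to 0.98. It is a reason to keep a likelihood model on all visits, and the categorical version keeps that benefit.

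**The categorical model's near-zero bias reflects dropout that is missing at random.** Correct. Protocol 7.6 foresees that "participants do not complete the study because of disease worsening, suggesting that data are not missing at random", and that case was not tested. The fix removes the time-shape error. It does not protect against informative dropout.

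**Protocol 7.6 commits more firmly to imputation or joint modelling.** It does so conditionally, and the SAP makes both optional.

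**The half condition needs equal dropout patterns.** Also correct. With unequal dropout and 3 to 5 points of curvature common to both arms, the contrast shifts by roughly 0.07 to 0.14.

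**Conclusion.** The point holds. On the SAP's wording the week-24 contrast is not the week-24 difference unless the arm difference is linear in time. At a true difference equal to the margin the time term moves the estimate by up to 0.77 points in either direction, and the model's own rate of declaring equivalence ranges from about 1% to 19% against a nominal 5%. In the reverse case a failure is a missed confirmation, not evidence of a difference.

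The weights are exact for complete data. The percentages depend on the assumed correlations and missing-data patterns and on trajectories the documents do not supply. The linear reading rests on time being in weeks and on the single slope reported from the same wording, since the SAP does not use the word continuous. The completely-at-random figures were obtained in separate calculations; the score-dependent ones rest on one set of simulations.

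The primary decision is untouched. This is a specification weakness in one sensitivity analysis. It is worth correcting because it blurs the comparison the analysis is there to provide.

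**What to change.** Leave the primary regression as it is. In the sensitivity model:

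- enter time as a category (nominal visits 0, 12, 24) with group-by-time terms;
- use a common baseline mean for both arms, or baseline as a covariate;
- use unstructured within-patient covariance, fitted by maximum likelihood to all observed visits;
- read the week-24 contrast against ±4.

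Only the first item removes the stated fault. On its own it costs precision: SE 0.96-1.14 against 0.93-1.12 for the linear model, 1-5% larger in every cell. The full package has SE 0.58-1.02, and that gain comes from the baseline constraint. The covariance takes six parameters instead of two.

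The work is one paragraph and one extra model on data already collected. The SAP was already signed, and its addendum records a change prompted by peer review dated 2024-04-17, so results may well be known. In that case add the model by dated addendum, report it beside the specified one and label it post hoc.

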7.5 Analysis Plan

Aim 1: To determine whether telehealth PC is equivalent to in-person PC for improving patients' QOL

We will begin with descriptive and graphical summaries of the endpoints to evaluate whether normality assumption is reasonable or if transformation is necessary. As the goal of the proposed study is to establish that patient-reported QOL with telehealth PC is equivalent to in-person PC, statistical testing for equivalence of the primary outcome will be two-sided with an alpha level of 0.05. We will use analysis of covariance (ANCOVA) models controlling for baseline values, and demographic and clinical factors (as necessary for any imbalances in baseline variables) to assess the effect of telehealth PC compared to in- person PC on QOL at 24 weeks. We will also use linear mixed models of the longitudinal data, allowing us to account for dependency among means over time and to control for demographic and clinical factors (as necessary for any imbalances in baseline variables) when examining change between groups in QOL across multiple time points (i.e., baseline, week-12, week-24, week-36, and week-48). Lastly, we will test Heterogeneity of Treatment Effect (HTE) based on age, gender, race, computer experience, and enrollment of caregivers using interaction terms in the linear mixed models (see HTE analysis plan).

We will use ANCOVA models controlling for baseline values, and demographic and clinical factors as necessary to assess the effect of telehealth PC compared to in-person PC on patient mood (HADS, PHQ-9), and coping strategies (Brief Cope subscales) at 24 weeks. We will then utilize linear mixed models of the longitudinal data as described above to examine change in depression and coping between groups across multiple time points. Lastly, we will also compare illness understanding as measured by the PTPQ between the two groups through week-24, analyzing items using linear or logistic regression as appropriate and adjusting for demographic and clinical factors as necessary. The patient's final post-baseline PTPQ assessment within 24 weeks will be used.

Aim 2: To determine whether telehealth PC is equivalent to in-person PC with respect to patient-clinician communication about EOL care preferences and length of stay in hospice

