- Patient depression symptoms, as measured by the PHQ-9

For each outcome, the difference in means at 24 weeks between intervention groups will be estimated using a linear regression model with group assignment (telehealth PC vs in-person PC) and baseline score as main effects. Model-based estimates of the mean with 95% CI in each group and the difference in means between groups and its 95% CI will be reported. In addition, for each outcome the rate of change across all study timepoints will be compared between groups using a linear mixed effects regression model with estimation via maximum likelihood. The model will include fixed effects for group assignment (telehealth vs in-person PC), time from baseline (in weeks), and time-by-group interaction, as well as random intercepts for each patient. Model-based estimates of the slope with 95% CI in each group and the difference in slopes between groups and its 95% CI will be reported.

Proportions of patient and caregiver prognostic understanding within 24 weeks, based on PTPQ items eliciting the goal of cancer care ("to cure my/my loved one's cancer" vs any other option) and the assessment of curability ("yes" vs "no") will be compared using generalized linear models specified with an identity link function and binomial response probability distribution. Model-based estimates of the proportion with 95% CI in each group and the difference in proportions between groups and its 95% CI will be reported.

Multiple metrics of healthcare utilization at the end of life will be compared between intervention groups among patients who die during the study. The number of emergency department visits and number of hospitalizations at the end of life will be compared using linear regression models or count regression models (e.g., Poisson, negative binomial) if the linear regression distributional assumptions are violated. The proportions of chemotherapy administration (any versus none) at the end of life will be compared using generalized linear models specified with an identity link function and binomial response probability distribution. Additionally, the occurrence of any emergency

department visit or any hospitalization at the end of life may be compared using these binomial models. Model-based estimates of the mean or proportion with 95% CI in each group and the difference in means or proportions between groups and its 95% CI will be reported.

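### The exploratory rate-of-change models allow random intercepts only, so if patients change at different rates their 95% intervals for slope differences are too narrow

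*SAP*

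**What the plan says.** SAP section 10, under Exploratory Outcomes, analyses the change in FACT-L from baseline to week 48 with a linear mixed model fitted by maximum likelihood. The fixed effects are group, time in weeks "and time-by-group interaction, as well as random intercepts for each patient. Model-based estimates of the slope with 95% CI in each group" are planned. The product is that "the difference in slopes between groups and its 95% CI will be reported".

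The same model is then set for the Brief COPE, CARGOQOL, caregiver HADS, patient HADS and PHQ-9: "the rate of change across all study timepoints will be compared between groups using a linear mixed effects regression model", again with random intercepts as the only random effect. These are exploratory outcomes 1, 3, 7, 9, 11 and 13 in SAP section 7. Protocol 7.5 gives the time points ("i.e., baseline, week-12, week-24, week-36, and week-48").

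The mixed model that accompanies the primary analysis (SAP section 10, Primary Outcome) uses baseline, week 12 and week 24 and has the same structure: "as well as random intercepts for each patient. A contrast will be used to estimate the difference in means at week 24". The SAP labels it a sensitivity analysis.

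None of these models is given a random slope, a different residual covariance or robust standard errors. The SAP addendum names robust standard errors once, for caregiver attendance at visits.

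**The concern.** A random-intercept model assumes that all patients in an arm share one true slope and that any two visits of a patient are equally correlated. If true slopes vary, that variation is pushed into the residual and only part of it returns in the standard error of the time-by-group term. The issue is the covariance structure, not the straight-line mean.

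The documents give reason to expect unequal slopes for quality of life. Protocol 1.2 says that about one-third of patients have tumour features that can carry a prognosis of several years, while most patients have a median survival of about one year. Protocol 7.6 supports its terminal-decline method by saying that it "controls for the known relationship between patient and caregiver QOL deterioration as the" patient's death approaches. Patients who reach that phase at different times will change at different rates over 48 weeks.

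At stake is the precision reported for the exploratory slopes. SAP section 9 says that exploratory results will emphasise estimates and confidence intervals, so the interval is the main product. Counting scales, there could be about 15 such comparisons: FACT-L 1, coping strategies 8, CARGOQOL 1, caregiver HADS 2, patient HADS 2, PHQ-9 1.

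**Working it through.** The plan states no standard error, power or slope variance for these comparisons, so there is no figure of its own to reproduce.

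**Inputs from the documents.** Visits at 0, 12, 24, 36 and 48 weeks (k = 5); n = 625 per arm; FACT-L SD 17.5 (SAP section 8) or 17.0 (protocol 7.4).

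**Assumed inputs.** Residual SD s = 10 points; between-patient slope SD t = 0.1 to 0.4 points per week; for the week-24 check, intercept SD 14 and no intercept-slope covariance.

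**Slope difference, complete data.** The mean visit time is 24, so Sxx = 24² + 12² + 0 + 12² + 24² = 1440.

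- True per-patient slope variance: s²/Sxx + t².
- Random-intercept model: the within-patient residual estimates s² + t²·Sxx/(k−1). Dividing by Sxx gives s²/Sxx + t²/4.
- The SE of the slope difference is √(2/625 × variance), multiplied by 48 for the 48-week scale.
- With s² = 100, s²/Sxx = 0.0694. Coverage = 2Φ(1.96 × reported/true SE) − 1.

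| t per week | t × 48 | true variance | model variance | true SE (48 wk) | reported SE (48 wk) | reported/true | coverage of 95% CI |
|---|---|---|---|---|---|---|---|
| 0.1 | 4.8 | 0.0794 | 0.0719 | 0.77 | 0.73 | 0.95 | 93.8% |
| 0.2 | 9.6 | 0.1094 | 0.0794 | 0.90 | 0.77 | 0.85 | 90.5% |
| 0.3 | 14.4 | 0.1594 | 0.0919 | 1.08 | 0.82 | 0.76 | 86.3% |
| 0.4 | 19.2 | 0.2294 | 0.1094 | 1.30 | 0.90 | 0.69 | 82.4% |

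The ratio does not depend on n, so a large trial does not cure it. At t = 0 the interval is correct.

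**Check by simulation.** With residual SD 9 and random dropout (70% observed at week 24, 48% at week 48), coverage was 94.0%, 94.9%, 91.8%, 84.0% and 83.9% at slope SDs of 0, 4, 8, 12 and 16 points per 48 weeks (1000 runs each). Direction and size agree with the closed form.

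**Plausibility of the range.** At t = 0.2 the slope contributes 0.2 × 24 = 4.8 points of SD at week 24, and 4.8²/17.5² = 7.5% of the variance. At t = 0.4 the implied week-48 SD is √(14² + 10² + 0.4² × 48²) = 25.8, far above 17.5. The documents do not fix the week-48 SD, but the top of the range is the least supported.

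**Week-24 contrast, visits 0, 12 and 24, complete data.** Here Sxx = 288.

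- True per-patient variance of the week-24 estimate: 196 + 576t² + (5/6)·100.
- Random-intercept model: 196 + (144 + 72)t² + (5/6)·100.
- False equivalence at the margin is 1 − Φ(1.645 × reported/true SE).

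| t | true | model | reported/true SE | coverage of 90% CI | false equivalence at the margin |
|---|---|---|---|---|---|
| 0.2 | 302.4 | 288.0 | 0.976 | 89.2% | 5.4% |
| 0.3 | 331.2 | 298.8 | 0.950 | 88.2% | 5.9% |
| 0.4 | 371.5 | 313.9 | 0.919 | 87.0% | 6.5% |

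With 70% observed at week 24, coverage is about 89.0%, 87.9% and 86.4%, and false equivalence 5.5%, 6.1% and 6.8%. A smaller intercept variance (114 instead of 196) lowers coverage to 88.7%, 87.2% and 85.3% and raises false equivalence to 5.7%, 6.4% and 7.3%.

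**The case against.** The strongest reply is that the size is conjecture. No slope variance is given for any outcome, and at 0.1 points per week the loss is about one percentage point of coverage. The passages pointing to unequal slopes concern prognosis and quality of life near death. They say nothing about the eight coping strategies, which are over half of the comparisons, and no calculation was made on the coping, HADS or PHQ-9 scales. Protocol 5.4 also stops assessments once a patient receives hospice services, so part of the late decline is never observed. All of this stands and limits the claim to a conditional one.

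Two stronger readings are tempting. A reader might infer that the false-positive rate of these comparisons is inflated. But the SAP lists no p-value for a slope difference and leaves exploratory outcomes unadjusted, so coverage is the right measure. A reader might also infer that the equivalence conclusion is at risk, because a narrow interval favours equivalence. But the primary decision rests on a linear regression at week 24 with baseline as covariate, which this does not touch, and the effect on the accompanying mixed model is small.

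The reply does not remove the core point. The structure is fully stated, it ignores slope variation that the protocol's own account makes likely for quality of life, and nothing else in the plan corrects it. The terminal-decline and partially conditional models are optional and address missing data.

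**Conclusion.** The point holds conditionally. If slopes vary between patients within an arm, the model-based 95% intervals for slope differences are too narrow. For residual SD 10 and five visits, true coverage is about 94%, 90%, 86% and 82% at slope SDs of 0.1 to 0.4 points per week. It becomes material from about 0.2, where the reported standard error is 0.85 of the true one. These figures rest on assumed variances and describe a scale like the FACT-L; they should not be read across to coping, HADS or PHQ-9. The documents do not show that every one of the roughly 15 intervals under-covers, only that the chosen model offers no protection if slopes differ.

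No primary or secondary conclusion changes. In the week-24 sensitivity model, 90% coverage falls to about 86–89% and false equivalence at the margin rises to about 5.5–7% at slope SDs of 0.2 to 0.4. It is worth correcting because intervals are what the SAP intends to emphasise for these outcomes.

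**What to change.** In both descriptions of the rate-of-change model under Exploratory Outcomes in SAP section 10, add a patient-level random slope for time with an unstructured 2×2 covariance, or use an unstructured covariance over the nominal visits. Make the same change to the week-24 mixed model under Primary Outcome for consistency.

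State a fallback: if the model does not converge, keep random intercepts and report patient-clustered robust standard errors. Say that this corrects the standard error only; it does not remove bias from dropout related to the outcome.

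The addendum already records changes made after the SAP was signed, including one prompted by peer review. Enter this as a dated item there, and if the slopes have already been estimated, report both sets of intervals.

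The cost is a sentence in the SAP and a small change to each model. Convergence may fail for some scales. Intervals widen only as far as slopes vary: by 1/0.85, about 17%, at a slope SD of 0.2 points per week, and hardly at all if slopes are alike.
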